No imputation will be performed for missing data. Participants who *do not know* or *prefer not to answer* a question used as an outcome variable will be treated as missing data. Survey entries which do not show a valid (positive or negative) SARS CoV-2 test result (N=111) in the Front Door Survey will not be included in the Front Door Survey Evaluable Population. Out of the 2,510 entries in the Front Door Survey, 425 completed survey items on key primary outcomes. Among the 1,313 respondents who consented to participate Baseline and End of Study Survey, 480 completed survey items on key secondary outcomes.

Analysis Objectives and Tasks

- Objective:** Summarize sociodemographic characteristics and medical history of participants in the Baseline Survey Evaluable Population and summarize sociodemographic and test-relevant characteristics of entries in Front Door Survey Evaluable Population

Analysis: Sociodemographic characteristics and medical history summaries will be presented in Table 1. All the sociodemographic characteristics and medical history variables from the Baseline Survey will be summarized by age category (Adult, Minor, Overall) where Adult is defined as age ≥ 18 years of age. Similarly, sociodemographic and test-relevant characteristics of entries will be presented in Table 5. All variables are categorical and will be summarized as counts and percentages. The denominators for the percentages for each variable in Table 1 are defined as the number of participants in the Baseline Survey Evaluable Population who have non-missing data for the variable. The denominators for the percentages for each variable in Table 5 are defined as the frequency of entries in the Front Door Survey Evaluable Population which have non-missing data for the variable.

- See Appendix for proposed:
 - Table 1: Participant Sociodemographic Characteristics and Medical History in Baseline Survey in Merced County, CA
 - Table 5: Sociodemographic and Test-relevant Characteristics in Front Door Survey Entries in Merced County, CA

- Objective:** Summarize self-reported COVID-19 testing characteristics and symptoms corresponding to the Baseline Survey Evaluable Population

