6. Objective: Model the association between social determinants of health (i.e., gender identity, employment, food/water/housing insecurity, and health insurance) and the following outcomes in the Baseline Survey Evaluable Population

- i) testing attitude (i.e., Participant thinks it's easy to get tested for COVID-19)
- ii) testing behavior (i.e., Participant has been tested for COVID-19)

Analysis: Social determinants of health and outcomes will be drawn from the Baseline Survey. For the outcome i) testing attitudes (i.e., Participant thinks it's easy to get tested for COVID-19), ordinal logistic regression will be used. For the outcome ii) testing behavior (i.e., Participant has been tested for COVID-19), logistic regression will be used. Odds ratio estimates and 95% confidence interval will be presented in Table 7.

The methods described above will constitute the main analysis of these secondary outcomes. The hypothesis is defined as:

$$H_0: \beta_i = 0$$

$$H_a: \beta_i \neq 0$$

And the logit is the linear function: $\ln(\frac{P}{1-P}) = \alpha + \beta_1x_1 + \beta_2x_2 + \dots + \beta_kx_k$

Where β_i is the parameter coefficient of independent variable x_i , and p represents the true probability that the dependent variable $y=1$ (event) given the numeric values on the independent variables. This analysis will be conducted using PROC LOGISTIC in SAS. The hypothesis as expressed above will be tested at a 2-sided significance level of 0.05

- See Appendix for proposed:
 - o Table 7: Regression estimates for the association between social determinants of health and COVID-19 testing attitude and behavior

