APPENDIX I - Proposed Table and Figure Listing

Table 1. Participant Sociodemographic Characteristics and Medical History in Baseline Survey in Merced County, CA

Characteristic	Minor (N=xxx)	Adult (N=xxx)	All Respondents (N=xxx) ^a
Age			
Median age in years	xx.x	xx.x	xx.x
(Missing)	xxx (xx.x%)	xxx (xx.x%)	xxx (xx.x%)
Race^b			
White	xxx (xx.x%)	xxx (xx.x%)	xxx (xx.x%)
Black or African American	xxx (xx.x%)	xxx (xx.x%)	xxx (xx.x%)
American Indian or Alaska Native	xxx (xx.x%)	xxx (xx.x%)	xxx (xx.x%)
Asian (including South Asian and Asian Indian)	xxx (xx.x%)	xxx (xx.x%)	xxx (xx.x%)
Native Hawaiian or Pacific Islander	xxx (xx.x%)	xxx (xx.x%)	xxx (xx.x%)
Some other race	xxx (xx.x%)	xxx (xx.x%)	xxx (xx.x%)
(Missing)	xxx (xx.x%)	xxx (xx.x%)	xxx (xx.x%)
Ethnicity			
Hispanic	xxx (xx.x%)	xxx (xx.x%)	xxx (xx.x%)
(Missing)	xxx (xx.x%)	xxx (xx.x%)	xxx (xx.x%)
Gender Identify			
Woman	xxx (xx.x%)	xxx (xx.x%)	xxx (xx.x%)
Man	xxx (xx.x%)	xxx (xx.x%)	xxx (xx.x%)
Non-binary	xxx (xx.x%)	xxx (xx.x%)	xxx (xx.x%)
Transgender man	xxx (xx.x%)	xxx (xx.x%)	xxx (xx.x%)
Transgender woman	xxx (xx.x%)	xxx (xx.x%)	xxx (xx.x%)
Gender nonconforming	xxx (xx.x%)	xxx (xx.x%)	xxx (xx.x%)
Agender	xxx (xx.x%)	xxx (xx.x%)	xxx (xx.x%)
Bigender	xxx (xx.x%)	xxx (xx.x%)	xxx (xx.x%)
(Missing)	xxx (xx.x%)	xxx (xx.x%)	xxx (xx.x%)
Current Pregnancy^c	N/A	xxx (xx.x%)	xxx (xx.x%)
(Missing)	N/A	xxx (xx.x%)	xxx (xx.x%)
Education			

Have never gone to school	xxx (xx.x%)	xxx (xx.x%)	xxx (xx.x%)
Completed 5 th grade or less	xxx (xx.x%)	xxx (xx.x%)	xxx (xx.x%)
Completed 6 th to 8 th grade	xxx (xx.x%)	xxx (xx.x%)	xxx (xx.x%)
Completed 9 th to 12 th grade	xxx (xx.x%)	xxx (xx.x%)	xxx (xx.x%)
Completed High school graduate or GED	xxx (xx.x%)	xxx (xx.x%)	xxx (xx.x%)
Completed Some college level/Technical/Vocational	xxx (xx.x%)	xxx (xx.x%)	xxx (xx.x%)
Completed Bachelor's degree	xxx (xx.x%)	xxx (xx.x%)	xxx (xx.x%)
Completed Master's/Doctoral degree	xxx (xx.x%)	xxx (xx.x%)	xxx (xx.x%)
(Missing)	xxx (xx.x%)	xxx (xx.x%)	xxx (xx.x%)
Household Member			
Just me	xxx (xx.x%)	xxx (xx.x%)	xxx (xx.x%)
Living with spouse, no kids	xxx (xx.x%)	xxx (xx.x%)	xxx (xx.x%)
Family including kids	xxx (xx.x%)	xxx (xx.x%)	xxx (xx.x%)
Family with 3 generations	xxx (xx.x%)	xxx (xx.x%)	xxx (xx.x%)
Family with 4 generations	xxx (xx.x%)	xxx (xx.x%)	xxx (xx.x%)
Living with roommates	xxx (xx.x%)	xxx (xx.x%)	xxx (xx.x%)
(Missing)	xxx (xx.x%)	xxx (xx.x%)	xxx (xx.x%)
Transitional Housing/Shelter/Homelessness			

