	Easy to get tested for COVID-19 ^a (N= xxx)		Has been tested for COVID-19 (N= xxx)	
	OR _{Adj} ^b	95% CI	OR _{Adj} ^c	95% CI
All Respondents^d (N= xxx)				
Gender Identify				
Woman	X.X	X.X - X.X	X.X	X.X - X.X
Man	X.X	X.X - X.X	X.X	X.X - X.X
Non-binary	X.X	X.X - X.X	X.X	X.X - X.X
Transgender man	X.X	X.X - X.X	X.X	X.X - X.X
Transgender woman	X.X	X.X - X.X	X.X	X.X - X.X
Gender nonconforming	X.X	X.X - X.X	X.X	X.X - X.X
Agender	X.X	X.X - X.X	X.X	X.X - X.X
Bigender
Transitional Housing/Shelter/Homelessness	X.X	X.X - X.X	X.X	X.X - X.X
Congregate Housing				
Group care setting	X.X	X.X - X.X	X.X	X.X - X.X
Nursing home	X.X	X.X - X.X	X.X	X.X - X.X
Residential care facility for disabled people	X.X	X.X - X.X	X.X	X.X - X.X
Psychiatric treatment facility	X.X	X.X - X.X	X.X	X.X - X.X
Group home	X.X	X.X - X.X	X.X	X.X - X.X
Board and care home	X.X	X.X - X.X	X.X	X.X - X.X
Prison or jail	X.X	X.X - X.X	X.X	X.X - X.X
Halfway house	X.X	X.X - X.X	X.X	X.X - X.X
Foster care	X.X	X.X - X.X	X.X	X.X - X.X
Homeless or in no consistent shelter

Loss of Employment due to COVID-19	X.X	X.X - X.X	X.X	X.X - X.X
Current employment status				
Working now	X.X	X.X - X.X	X.X	X.X - X.X
Temporarily laid off/sick leave/maternity leave	X.X	X.X - X.X	X.X	X.X - X.X
Unemployed	X.X	X.X - X.X	X.X	X.X - X.X
Retired	X.X	X.X - X.X	X.X	X.X - X.X
Permanently/temporarily disabled	X.X	X.X - X.X	X.X	X.X - X.X
Keeping house	X.X	X.X - X.X	X.X	X.X - X.X
Student	X.X	X.X - X.X	X.X	X.X - X.X
Other
Health Insurance				
No health insurance	X.X	X.X - X.X	X.X	X.X - X.X
Private insurance	X.X	X.X - X.X	X.X	X.X - X.X
Public insurance (Medicare/Medicaid/Tricare)
Loss Health Coverage due to COVID-19 Pandemic	X.X	X.X - X.X	X.X	X.X - X.X
Getting the Needed Health Care during COVID-19 Pandemic				
No, not a challenge	X.X	X.X - X.X	X.X	X.X - X.X
Yes, a minor challenge	X.X	X.X - X.X	X.X	X.X - X.X
Yes, this is a major challenge
Have A Place to Stay/Live during COVID-19 Pandemic				
No, not a challenge	X.X	X.X - X.X	X.X	X.X - X.X
Yes, a minor challenge	X.X	X.X - X.X	X.X	X.X - X.X
Yes, this is a major challenge
Getting Enough Food to Eat during COVID-19 Pandemic				
No, not a challenge	X.X	X.X - X.X	X.X	X.X - X.X

Yes, a minor challenge	X.X	X.X - X.X	X.X	X.X - X.X
Yes, this is a major challenge
Having Clean Water to Drink during COVID-19 Pandemic				
No, not a challenge	X.X	X.X - X.X	X.X	X.X - X.X
Yes, a minor challenge	X.X	X.X - X.X	X.X	X.X - X.X
Yes, this is a major challenge
Getting the Needed Medicine during COVID-19 Pandemic				

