No, not a challenge	X.X	X.X - X.X	X.X	X.X - X.X
Yes, a minor challenge	X.X	X.X - X.X	X.X	X.X - X.X
Yes, this is a major challenge
Getting to Needed-to-Go Place during COVID-19 Pandemic				
No, not a challenge	X.X	X.X - X.X	X.X	X.X - X.X
Yes, a minor challenge	X.X	X.X - X.X	X.X	X.X - X.X
Yes, this is a major challenge

Note:

NA=odds ratio not estimable due to small sample sizes.

Bolded estimates p<.05.

^aEasy to get tested for COVID-19^a per one unit change (Strongly disagree to Disagree, Disagree to Neither disagree or agree; Neither disagree or agree to Agree; Agree to Strongly agree).

^bEstimates based on ordinal logistic regression, adjusted for gender identity.

^cEstimates based on binary logistic regression, adjusted for gender identity.

^dNumber of All respondents is the number of participants who have complete data on full set of social determinants of health factors (i.e., gender identity, food/water/housing insecurity, employment, and health insurance), sample size on each outcome could vary based on the number of participants respond to the relevant survey item.

History of Changes to this Document

Version	Date	Description of Change(s)
1.0	03 March 2022	Initial draft
2.0	30 April 2022	Revision based on PIs' comments

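### Table 7 gives Congregate Housing no level for people in ordinary homes, so its odds ratios compare congregate settings only with homelessness

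*SAP*

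**What the plan says.** Objective 6 of the SAP models social determinants of health against "the following outcomes in the Baseline Survey Evaluable Population": whether the participant finds it easy to get tested, and whether the participant has been tested. The results go to Table 7 in Appendix I.

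- **The factor.** Congregate Housing in Table 7 has ten rows, running from group care and nursing homes through prison and foster care to "Homeless or in no consistent shelter". The last row has no estimate cells and so is the reference. Table 1 shows the same ten rows followed only by a missing row.
- **Ordinary homes.** Table 1 records these under a separate item, Household Member, with answers such as "Living with spouse, no kids". That item is not in Table 7.
- **The analysed respondents.** Table 7 note d defines them as "participants who have complete data on full set of social determinants of health factors", and spells the factors out as "gender identity, food/water/housing insecurity, employment, and health insurance". It adds that N may vary by outcome.
- **Missing data.** The section on handling missing data states: "No imputation will be performed for missing data". Its rule on don't-know and prefer-not-to-answer responses covers "a question used as an outcome variable will be treated as missing data"; covariates are not mentioned.
- **Adjustment.** Table 7 notes b and c adjust the estimates for gender identity only.

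**The concern.** The test kits went to community households, so many Baseline respondents can be expected to live in ordinary homes. Those people are neither a level of the congregate-housing factor nor its comparator. The natural question, whether people in congregate settings differ from everyone else in access to testing, cannot be answered from a table whose only comparator is homelessness.

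There is also a possible knock-on effect. A respondent with no valid value on one factor fails a complete-data rule that spans all factors. If that rule reaches Congregate Housing, the rows on insurance, employment, food, water and access to care could also lose the respondents whom Objective 6 is about.

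**Working it through.** **1. Layout of Table 7.** Levels per factor, in table order: gender identity 8; transitional housing yes/no 2; Congregate Housing 10; loss of employment 2; employment status 8; health insurance 3; loss of coverage 2; six challenge items with 3 each. That is 13 factors. Coefficients beyond the reference: 7 + 1 + 9 + 1 + 7 + 2 + 1 + (6 × 2) = 40. Nine of the 40 belong to Congregate Housing.

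**2. How could an ordinary-home resident be coded?** There are three possibilities:
- *Missing.* The person cannot enter a model containing this factor. The nine odds ratios compare congregate settings with homelessness, among congregate and homeless respondents only.
- *An eleventh level that is not printed.* The person is in the model, but the nine printed odds ratios still have homelessness as reference, and the table has no row for ordinary homes.
- *Ten separate yes/no items.* Each setting would then have its own odds ratio against not ticked, and the homeless row would not be an empty reference row. Table 7 is not laid out this way, and Table 1 note b names only race and health conditions as tick-all items.

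Under none of these does Table 7 as printed compare congregate settings with ordinary homes.

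**3. Outcome counts.** From the missingness Table 2 in the SAP's Study Population section, out of 1,208:
- has been tested: 1,208 − 216 = 992, as printed;
- accessibility to testing, taken here as the item behind ease of getting tested: 1,208 − 218 = 990, as printed.

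These are the ceilings for Table 7, about 82% of 1,208.

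**4. The conditional loss across the whole table.** Suppose note d's complete-data set includes Congregate Housing and ordinary-home respondents are coded missing on it. Let s be the share in a listed congregate or homeless category. The documents do not give s, so these values are assumptions. Before any other missingness, retained N = s × 990 (or 992):

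| s | Retained of 990 | Retained of 992 |
|---|---|---|
| 1% | 10 | 10 |
| 5% | 50 | 50 |
| 10% | 99 | 99 |
| 20% | 198 | 198 |

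More than half is lost whenever s is below 50%. If either condition fails, this loss is zero.

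**5. The complete-data rule once the factor is repaired.** If each of the other 12 factors had independent non-response m (assumed), the full-set rule would keep (1 − m)^12: 0.785 at 2% and 0.540 at 5%. A model with gender identity and one factor needs (1 − m)^2: 0.960 and 0.9025. The standard error ratio is √(0.960/0.785) = 1.11 and √(0.9025/0.540) = 1.29. This is the unfavourable end. In the SAP's missingness table the counts cluster (642, 643, 642; 216, 218; 375, 376). If the same people skip a whole block, both rules keep about 1 − m and the ratio is close to 1.

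**The case against.** A reader might infer that the plan drops most Baseline respondents from all of Table 7. The documents do not support that as a finding, for three reasons.

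- Note d's list says housing insecurity and does not name congregate housing. The list pairs housing with food and water, which Table 7 carries as challenge items. The matching item is having a place to stay, which has a valid answer for anyone in an ordinary home.
- The coding of ordinary-home respondents is not shown, and the survey instrument is not in the documents. Non-selection can be stored as non-missing: the vaccine-reason items, which are tick-all, show 0 missing of 1,208. The workplace items, with 642 to 643 missing, are consistent with the opposite practice, so the evidence is mixed.
- Notes b and c suggest one factor per model. If note d is only a header count, a coding gap in Congregate Housing affects that factor's rows alone.

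All three points stand, and they make the table-wide loss conditional.

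It can also be said that the SAP's tables often omit a null row. Table 1 prints Hispanic and then a missing row, yet Table 6 uses non-Hispanic as a valid reference. That analogy covers yes/no items whose other level is obvious. It does not carry over to a factor with ten printed levels and its own printed reference row.

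Finally, a common complete-case sample is a legitimate choice that keeps all estimates on the same people, and Table 6 note e does the same. The table already expects some odds ratios not to be estimable. Housing is also covered in Table 7 by the transitional-housing and place-to-stay items, so the gap concerns one factor and not the whole housing topic.

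**Conclusion.** The defect in the Congregate Housing factor holds on every reading of the table. As printed, its nine odds ratios are contrasts with homelessness, ordinary-home residents have no row, and the factor cannot be assessed in the population that Objective 6 names. This needs no assumption beyond reading the empty row as the reference, which is how the other multi-level factors in Tables 6 and 7 are laid out.

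The effect on the remaining rows is a risk, not an established result. It needs both that note d's set includes this factor and that ordinary-home respondents are coded missing. The SAP states neither. If both hold, about 10 to 99 respondents would remain at an assumed share of 1% to 10%.

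The cost of a common complete-case sample in itself is a secondary matter. The 11% to 29% wider standard errors depend on assumed, independent non-response and would shrink if non-response is clustered.

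**What to change.** 1. Add a level for not being in congregate housing, make it the reference in Table 7, and show it in Table 1. Code to it the respondents who reached the item and selected none of the settings. Alternatively, collapse the factor to a yes/no indicator of any congregate setting.
2. If the data cannot separate that level from non-response, take Congregate Housing out of note d's complete-data set.
3. In note d, list exactly which Table 7 factors define the complete-data set, and print the N retained against 1,208.
4. State whether Table 7 holds one joint model or one model per factor, and how not-applicable answers are coded for covariates.
5. Because the stated adjustment is for gender identity only, also report each factor's odds ratio on all respondents with data on the outcome, that factor and gender identity, beside the common complete-case result.

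The cost is one recoded variable, one added table row (or a collapsed factor), a reworded note and a second set of estimates. No new data are needed. The small downside is that N will differ between factors in the second set.
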